4.6 TIMING OF STUDY ASSESSMENTS

4.6.1 Screening/Baseline (Visit 1)

The following standard of care assessments performed prior to obtaining informed consent will be used in the screening process. Once consent is obtained, the results of the standard of care assessments may be used for the study.

- Medical history
- Demographics
- Neurological examination
- Vital signs
- Complete blood count without differential
- Coagulation status
- Pregnancy test (serum or urine)
- Serum blood glucose
- Non-contrast CT scan or MRI, including DW MRI, either SW or GRE, and FLAIR images
- NIHSS score (Note: This must be performed by an NIHSS-certified practitioner; see [Appendix 7](#))
- Concomitant medications

All screening evaluations with the exception of certain laboratory results (e.g., coagulation and complete blood count) must be completed and reviewed to confirm that patients have met all eligibility criteria prior to treatment. Serum glucose is required to confirm eligibility prior to enrollment; however, if the investigator feels there is clinical suspicion that would be related to an exclusion laboratory test that would preclude the patient from eligibility, the results of those laboratory tests must be obtained prior to treatment.

The investigator will maintain a screening log to record details of all patients consented to confirm eligibility or record reasons for screening failure, as applicable.

4.6.2 Visit 2 (22 to 36 Hours after Treatment Initiation)

A non-contrast cranial CT or MRI (including DW MRI, either SW or GRE, FLAIR, and T1 and T2 sequences) will be performed at 22 to 36 hours after treatment with study drug has been initiated (bolus). Either a CT scan or MRI may be performed, as consistent with the institutional standard of care; the main criterion is to perform radiographic imaging of the brain by a modality sensitive to the presence of blood. An NIHSS will also be performed during this visit, but prior to review of the imaging results (or by an

investigator blinded to the results). AEs¹ and concomitant medications will also be assessed at this visit.

4.6.3 Visit 3 (Day 5 or Discharge from Hospital, if Sooner than Day 5)

On Day 5 (or discharge from hospital, if sooner than Day 5), NIHSS score, stroke etiology, AEs, and concomitant medications will be collected. Discharge location will be collected at the time of hospital discharge.

4.6.4 Visit 4 (Day 30 [30 ± 7 Days])

A phone call to the patient or caregiver will be made at Day 30 and an mRS will be assessed (see [Appendix 8](#)). AEs, concomitant medications, and patient survival will be assessed during this phone visit. Pregnancy will also be assessed for female patients of childbearing potential.

4.6.5 Visit 5 (Day 90 [± 14 Days])/Study Completion)

Primary and secondary efficacy endpoints, as well as all exploratory endpoints, will be assessed at Day 90 with the patient. The following assessments will be performed:

- NIHSS score ([Appendix 7](#))
- Patient survival
- mRS ([Appendix 8](#))
- GOS ([Appendix 9](#))
- BI ([Appendix 10](#))
- EQ-5D ([Appendix 4](#))
- SIS-16 ([Appendix 5](#))
- CES-D ([Appendix 6](#))
- Cognitive assessments ([Appendix 11](#))
 - Controlled Oral Word Association test
 - HVLT-R trials 1, 2, and 3
 - Digit symbol coding from the WAIS III
 - Forward and Backward Digit Span test
 - Benton Judgment of Line Orientation test, form V
 - HVLT-R trial 4 and recognition
 - Animal Naming test

¹ AE/SAE collection should be started as soon as study drug administration (bolus) is initiated.

- BNT 15-item short form

The above cognitive assessments will be provided in Spanish for those patients requiring translations with the exception of the BNT 15-item short form.

- Walking speed ([Appendix 12](#))
- Concomitant medications
- SAEs and certain AEs (See Section [5.3.1](#))

4.6.6 Early Discontinuation

Concomitant medication, AEs, and patient survival will be assessed via a phone call, if possible.

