4.1.2 Exclusion Criteria

Patients who meet any of the following criteria will be excluded from study entry:

- CT or MRI findings consisting of one of the following:
 - CT with clear large hypodensity that is greater than one-third middle cerebral artery (MCA) territory (or greater than 100 cc if not in MCA territory),
 - MRI with clear large hyperintensity on concurrent diffusion-weighted (DW) and fluid-attenuated inversion recovery (FLAIR) that is greater than one-third MCA territory (or greater than 100 cc if not in MCA territory),
 - Imaging lesion consistent with acute hemorrhage of any degree, OR
 - Evidence of intraparenchymal tumor
- Disability prior to the presenting stroke (historical mRS score ≥ 2)
- Standard contraindications to IV alteplase for patients treated within 3 hours of symptom onset, including:
 - Head trauma or previous stroke within the previous 3 months
 - Myocardial infarction within the previous 3 months
 - Gastrointestinal or urinary tract hemorrhage within the previous 21 days
 - Major surgery within the previous 14 days
 - Arterial puncture at a non-compressible site within the previous 7 days
 - Any history of ICH with the exception of <5 chronic microbleeds on MRI
 - Elevated blood pressure (systolic >185 mm Hg or diastolic >110 mm Hg), or the use of aggressive measures (use of more than two intravenous agents to lower blood pressure) to achieve blood pressure within acceptable parameters
 - Treatment with unfractionated heparin within the last 48 hours and activated partial thromboplastin time (aPTT) outside of the normal range as specified by the center's local laboratory
 - Blood glucose <50 mg/dL
 - International normalized ratio (INR) >1.7 (Note: This does not need to be verified prior to randomization if there is no clinical suspicion of abnormality.)
 - Platelet count of $<100,000/\text{mm}^3$ (Note: This does not need to be verified prior to randomization if there is no clinical suspicion of abnormality.)
 - Treatment with a direct thrombin inhibitor or factor Xa inhibitor (including novel oral anticoagulants [e.g., dabigatran, rivaroxaban, apixaban, edoxaban]) within the last 48 hours
 - Treatment with a low-molecular-weight heparin (e.g., dalteparin, enoxaparin) within the last 48 hours
- Allergic reactions to study drug, aspirin, *or* nonsteroidal anti-inflammatory drugs (NSAIDs)

Alteplase—Genentech, Inc.
33/Protocol ML29093, Version 3

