4.7 PATIENT, TREATMENT, STUDY, AND SITE DISCONTINUATION

4.7.1 Patient Discontinuation

Patients have the right to voluntarily withdraw from the study at any time and for any reason. In addition, the investigator has the right to withdraw a patient from the study at any time. Reasons for withdrawal from the study may include, but are not limited to, the following:

- Patient withdrawal of consent at any time
- Any medical condition that the investigator or Sponsor determines may jeopardize the patient's safety if he or she continues in the study
- Investigator or Sponsor determines it is in the best interest of the patient
- Patient non-compliance, specifically defined as unwillingness to participate in a 3-month assessment of neurological status and function

Every effort should be made to obtain information on patients who withdraw from the study. The primary reason for withdrawal from the study should be documented on the appropriate eCRF. However, patients will not be followed for any reason after consent has been withdrawn. Patients who withdraw from the study will not be replaced.

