6.1 DETERMINATION OF SAMPLE SIZE

A sample size of 856 is required in order to achieve 80% power in the primary analysis to detect an effect size of 9% absolute difference in the proportion of patients with favorable outcomes between the alteplase and control arms. The above sample size calculation assumes a control proportion of 65% and Type I error probability of 0.025 (one-sided), and uses a group sequential design with one interim analysis for futility (non-binding), based on an O'Brien-Fleming boundary, after 50% of the anticipated sample size have completed the 90-day follow-up assessments. [REDACTED] was used for this sample size calculation.

The ITT principle will be applied to the primary analysis and, therefore, to safeguard against dilution of the treatment effect associated with an approximate 5% non-adherence rate (due to lost to follow-up, consent withdrawal, treatment crossovers, and stroke mimics), the above sample size needs to be inflated by a factor of 1/0.95² or 1.108 ([Friedman et al. 1998](#)). Therefore, a total sample size of 948 is required for this study.

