Appendix 1 (cont.) Schedule of Assessments

- ^a Includes smoking history and stroke history.
- ^b A partial neurological examination is to be performed for each patient. The NIHSS will be a component of the neurological examination and will be performed only by practitioners who are certified to perform an NIHSS assessment. Additional, or supplemental, neurological exams will also be performed, including assessment of mental status, cranial nerves, motor function and coordination.
- ^c Includes pulse and systolic/diastolic blood pressure (while patient is in a supine position). *Record abnormalities on the Adverse Event eCRF.*
- ^d Complete blood count includes hemoglobin, hematocrit, white blood cell count, and platelet count.
- ^e Coagulation status includes INR values of >1.7, activated partial thromboplastin time, patient or family report of patient currently taking an oral anticoagulant (e.g., dabigatran, rivaroxaban, apixaban, edoxaban), or patient or family report of patient currently taking a low-molecular-weight heparin (e.g., dalteparin, enoxaparin) within the last 48 hours.
- ^f Pregnancy status will be determined in women of childbearing potential. Serum or urine pregnancy test can be collected.
- ^g Serum glucose (values of <50 mg/dL are contraindicated for alteplase).
- ^h MRI or CT scan should be performed if any clinical findings suggest ICH.
- ⁱ NIHSS score should be assessed and recorded at the time of any clinical findings that suggest ICH.
- ^j The mRS may be performed by telephone, if necessary, for visits on Days 30 and 90.
- ^k The BI, CES-D, EQ-5D, and SIS-16 can be administered by phone interview if an in-person patient visit cannot be scheduled in the allotted time.
- ^l Assessments include: Controlled Oral Word Association test; HVLT-R trials 1, 2, and 3; digit symbol coding from the WAIS III; Forward and Backward Digit Span test; Benton Judgment of Line Orientation, form V; HVLT-R trial 4 and recognition; semantic fluency (Animal Naming test); and BNT (15-item short form).
- ^m Assessment of walking speed requires an in-person patient visit and is best combined with administration of the BI, CES-D, EQ-5D, and SIS-16.
- ⁿ Concomitant medications include any prescription medications or over-the-counter preparations used by the patient within 7 days prior to screening.

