
Administer stroke scale items in the order listed. Record performance in each category after each subscale exam. Do not go back and change scores. Follow directions provided for each exam technique. Scores should reflect what the patient does, not what the clinician thinks the patient can do. The clinician should record answers while administering the exam and work quickly. Except where indicated, the patient should not be coached (i.e., repeated requests to patient to make a special effort).
		
1	
Has the subject had a stroke (either as the index event at randomization or as an outcome event)? If no, form is complete.
	
 No  Yes

2	(1a) Level of Consciousness	
 0=Alert; keenly responsive  1=Not alert, but arousable by minor stimulation to obey, answer or respond  2=Not alert, requires repeated stimulation to attend, or is obtunded and requires strong or painful stimulation to make movements (not stereotyped)  3=Responds only with reflex motor or autonomic effects or totally unresponsive, flaccid, areflexic (Complete form using coma scoring)

3	(1b) LOC Questions	
 0=Answers both questions correctly  1=Answers one question correctly  2=Answers neither question correctly

4	(1c) LOC Commands	
 0=Performs both tasks correctly  1=Performs one task correctly  2=Performs neither task correctly

5	(2) Best Gaze	
 0=Normal  1=Partial gaze palsy. This score is given when gaze is abnormal in one or both eyes, but where forced deviation or total gaze paresis are not present  2=Forced deviation, or total gaze paresis not overcome by the oculocephalic maneuver

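### Treated patients can be withdrawn from outcome follow-up without withdrawing consent, the discontinuation call omits the mRS, and the NIHSS form stops for stroke mimics

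*Protocol*

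**What the plan says.** All references are to protocol Version 3.

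- **Withdrawal from the study (Section 4.7.1).** Besides withdrawal of consent, the listed reasons include a medical condition that the investigator or Sponsor thinks makes continuing unsafe, a judgment by either that leaving is in the patient's best interest, and "Patient non-compliance, specifically defined as unwillingness to participate in a 3-month assessment of neurological status and function". The section also asks sites to try to obtain information on patients who withdraw. It bars follow-up only once consent has been withdrawn.
- **Stopping study drug (Section 4.7.2).** These patients stay in the study to Day 90, with ITT given as the reason. Section 4.2 likewise keeps unblinded patients in for all visits.
- **The discontinuation call (Section 4.6.6).** "Concomitant medication, AEs, and patient survival will be assessed via a phone call, if possible". The Early Discontinuation column of Appendix 1 adds discharge location, but has no mark for the mRS.
- **Telephone mRS (Appendix 1, footnote j).** "The mRS may be performed by telephone, if necessary, for visits on Days 30 and 90". Section 4.6.4 already plans the Day 30 mRS as a call to the patient or caregiver.
- **NIHSS form (Appendix 7, item 1).** "Has the subject had a stroke (either as the index event at randomization or as an outcome event)? If no, form is complete".
- **Analysis (Sections 6.1, 6.2 and 6.6).** All randomized patients are analyzed. Stroke mimics are named in the 5% non-adherence allowance. Missing data are multiply imputed with the last observation, for example the Day 30 mRS, among the predictors.

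**The concern.** Treatment is one infusion of about an hour and one tablet, and the bolus itself marks enrollment (Section 4.2). For almost all of the 90 days, therefore, withdrawing a patient from the study removes no exposure to study drug; it only ends outcome collection. A worsening medical condition, or reluctance to be assessed, is plausibly related to the outcome, so the missing values may be informative. That is the situation in which imputation most needs a post-stroke measurement of the same scale, and the planned call does not take one.

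The NIHSS stop rule is a second, smaller gap. Mimics are expected in the ITT set, and NIHSS 0–1 is one of four components of the secondary global outcome (Section 2.2), but the form collects no item scores for them.

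**Working it through.** **1. The plan's own figures.** The inputs are in Section 6.1: "Type I error probability of 0.025 (one-sided"), "A sample size of 856 is required in order to achieve 80% power in the primary analysis", and an "effect size of 9% absolute difference in the proportion of patients with favorable outcomes" from a control rate of 65%, so 65% against 74%.

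- Fixed design, unpooled variance: 0.65 × 0.35 + 0.74 × 0.26 = 0.4199. Per arm, (1.960 + 0.842)² × 0.4199 / 0.09² ≈ 407, total about 814.
- One non-binding futility look at 50% with O'Brien-Fleming-type beta spending multiplies this by 1.052, giving 856.5. The stated 856 reproduces.
- Inflation: 856 / 0.95² = 948.5. The stated 948 reproduces.

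The sample size is not in question, and the fix does not change it.

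**2. The rules side by side.**

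| Patient | Followed to Day 90? | mRS collected on leaving? |
|---|---|---|
| Stops study drug early (4.7.2) | Yes | Not needed |
| Is unblinded (4.2) | Yes | Not needed |
| Withdrawn by investigator or Sponsor judgment (4.7.1) | No rule requires it | No (4.6.6, Appendix 1) |
| Withdraws consent (4.7.1) | Barred, properly | Not after withdrawal |

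The third row is the avoidable loss.

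**3. What imputation has to work with.** Appendix 1 schedules the mRS at Days 30 and 90 only. A patient who leaves before Day 30 contributes the NIHSS at 22–36 hours and at Day 5 or discharge, if reached, but no post-stroke mRS.

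**4. Sensitivity of power (illustration, assumed rates).** Assume equal missingness in both arms, 474 per arm, fixed-design power, ignoring the futility look:

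| Missing mRS | Observed cases | Missing counted unfavorable |
|---|---|---|
| 0% | 85.4% | 85.4% |
| 2% | 84.7% | 83.1% |
| 5% | 83.6% | 79.5% |
| 10% | 81.6% | 73.2% |

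These rates are not estimates of the loss. Loss of power is modest at low rates; bias, if leaving depends on outcome or arm, is the larger worry and cannot be quantified from the protocol.

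**The case against.** The strongest replies are these.

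- **Section 4.7.1 already asks for every effort to obtain information, and Day 90 mRS by telephone is already allowed.** True, and it softens the point. But the general sentence names no mRS, and the discontinuation schedule gives it no place. A patient who will not travel can be reached by telephone only if not first withdrawn for non-compliance. A patient who refuses the assessment itself cannot be captured by any rule.
- **An mRS at an early call is not the Day 90 endpoint.** This stands. It is an intermediate value for imputation; only continued follow-up recovers the endpoint.
- **The analysis plan may set a score for mimics.** It may, and item 1 identifies them, but no plan can recover item scores that the form did not collect. A reader might further infer that treatment influences who is called a mimic; nothing in the protocol shows that.

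A reader might also draw stronger conclusions that the document does not support.

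- *That last observation carried forward would use the pre-stroke score*, which eligibility keeps below 2 ("Disability prior to the presenting stroke (historical mRS score" of 2 or more excludes). Section 6.6 does not say so; it gives the Day 30 mRS as its example.
- *That the 5% allowance, about 47 of 948 patients, is a missing-mRS rate.* It also covers crossovers and mimics, who can still have a Day 90 mRS, and it does not name withdrawal by investigator or Sponsor judgment.
- *That extreme imputations would move the treatment effect by several points.* With 5% missing in both arms, all favorable gives (0.95 × 74 + 5) − (0.95 × 65 + 5) = 8.55 points; all unfavorable gives 0.95 × 74 − 0.95 × 65 = 8.55. The difference is the same. The two supportive analyses in Section 6.6 are not at fault.

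**Conclusion.** The point holds as a matter of avoidable missing data. Section 4.7.1 permits loss of follow-up that Section 4.7.2 forbids for a closely related group; the planned call omits the scale of the primary endpoint although the protocol accepts it by telephone; and Appendix 7 leaves mimics without an NIHSS score, which affects the secondary global outcome and the exploratory NIHSS but not the primary endpoint.

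Its size is unknown. The protocol gives no rate for withdrawal without withdrawal of consent, none for leaving before Day 30, and none for mimics alone. That such missingness is informative is a reasonable assumption from the listed reasons, not something the protocol demonstrates. This is a cheap improvement worth making; it does not show that the planned analysis is biased or underpowered.

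**What to change.** 1. In Section 4.7.1, state that every treated patient stays in Day 90 outcome follow-up, by telephone mRS if needed, unless consent for follow-up is withdrawn. The existing bar after withdrawal of consent stays.
2. Add a telephone mRS to Section 4.6.6 and to the Early Discontinuation column of Appendix 1. Label it an intermediate value for the imputation model, not a substitute for the Day 90 mRS.
3. In Appendix 7, item 1, delete the instruction that ends the form when the answer is no, so that the NIHSS is scored for every ITT patient. Keep the question, so that mimics remain identifiable.

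The cost is a few minutes on calls and edits to wording and one form. The planned sample size is unchanged.

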4.7 PATIENT, TREATMENT, STUDY, AND SITE DISCONTINUATION

4.7.1 Patient Discontinuation

Patients have the right to voluntarily withdraw from the study at any time and for any reason. In addition, the investigator has the right to withdraw a patient from the study at any time. Reasons for withdrawal from the study may include, but are not limited to, the following:

- Patient withdrawal of consent at any time
- Any medical condition that the investigator or Sponsor determines may jeopardize the patient's safety if he or she continues in the study
- Investigator or Sponsor determines it is in the best interest of the patient
- Patient non-compliance, specifically defined as unwillingness to participate in a 3-month assessment of neurological status and function

Every effort should be made to obtain information on patients who withdraw from the study. The primary reason for withdrawal from the study should be documented on the appropriate eCRF. However, patients will not be followed for any reason after consent has been withdrawn. Patients who withdraw from the study will not be replaced.

4.7.2 Study Treatment Discontinuation

The study intervention should be discontinued if the patient displays symptoms concerning sICH during the infusion of the study drug. Prompt imaging should be done to assess for ICH. If ICH is seen, study drug infusion should not be resumed and the treatment assignment may be unblinded if blood products (to reverse the biological activity of IV alteplase) are indicated. If ICH is not seen, study drug infusion should immediately be restarted *in order to complete the infusion within 4 hours after the last known well time at the same rate as the previous infusion until the remainder of study drug is infused.*

Patients must discontinue study treatment if they experience any of the following:

- Anaphylactoid reaction (including angioedema)
- Serious bleeding (not controllable by local pressure) at puncture site or serious bleeding in a critical location (e.g., intracranial, gastrointestinal, retroperitoneal, pericardial)

The primary reason for study treatment discontinuation should be documented on the appropriate eCRF. Patients who discontinue study treatment prematurely will not be replaced. Patients who discontinue study treatment prematurely will continue in the study and be followed through Day 90, based on the intent-to-treat (ITT) principle.

4.7.3 Study and Site Discontinuation

The Sponsor has the right to terminate this study at any time. The Sponsor will notify the investigator if the Sponsor decides to discontinue the study. Reasons for terminating the study may include, but are not limited to, the following:

- The incidence or severity of AEs in this or other studies indicates a potential health hazard to patients.
- Patient enrollment is unsatisfactory
- A pre-specified boundary at the interim analysis was crossed

The Sponsor has the right to close a site at any time. Reasons for closing a site may include, but are not limited to, the following:

- Excessively slow recruitment
- Poor protocol adherence
- Inaccurate or incomplete data recording
- Non-compliance with the International Conference on Harmonisation guideline for Good Clinical Practice
- No study activity (i.e., all patients have completed study assessments and all obligations have been fulfilled)

